1.1. List of Abbreviations

AE	Adverse Event
AHI	Apnea Hypopnea Index
APAP	Automatic Positive Airway Pressure
Bi-level PAP	Bi-level Positive Airway Pressure
CIA	Clinical Investigation Administration
CIP	Clinical Investigation Plan
CPAP	Continuous Positive Airway Pressure
CRF	Case Report Form
FPH	Fisher & Paykel Healthcare
GCP	Good Clinical Practice
HA	Hazard Analysis
IB	Investigators Brochure
ICF	Informed Consent Form
ICH	International Conference on Harmonization of Technical Requirements for Registration of Pharmaceuticals for Human Use
IRB	Independent Review Board
NTLSC	North Texas Lung & Sleep Clinic
OSA	Obstructive Sleep Apnea
PAP	Positive Airway Pressure
SAE	Serious Adverse Event
UI	User Instructions

2. Document Information

2.1. Purpose and Scope

The purpose of the trial is to evaluate the performance, comfort and ease of use of the F&P Nasal Mask in the home environment.

2.4. Monitoring Arrangements

FPH will be conducting the study, and as such the investigators or their nominees will monitor the progress of the investigation. The principal investigator will have access to all source documents needed to verify the entries on the Case Report Forms (CRF) and other protocol related documents; provided that participant confidentiality is maintained in agreement with local regulations. It will be the principal investigator's responsibility to inspect the CRF at regular intervals throughout the investigation, to verify the adherence to the protocol and the completeness, consistency and accuracy of the data being entered on them.

The investigator's file will contain the protocol/amendments, financial disclosure form, CRFs and data clarification and query forms, Independent Review Board (IRB) approval with correspondence, informed consent, staff curriculum vitae and authorization forms, screening and enrolment logs, and other appropriate documents/ correspondence as per International Conference on Harmonization (ICH) and Good Clinical Practice (GCP) and local regulations.

2.5. Data Management

Data obtained for this investigation will be recorded in source documents and attached to the CRF for both the administration of the study and collection of participant data.

Original CRFs will be stored for 15 years by FPH. Copies of the CRF will be stored on site at Clinical trial of Florida (CTF) for 15 years.

3. Investigator Information

5.1. Identification of the Medical Device

The F&P Nasal is a Nasal masks primarily used in sleep laboratories and in home use for the treatment of OSA using CPAP devices.

5.2. Device Risk Analysis and Management

Positive airway pressure (PAP) therapy via a nasal or oronasal mask is standard clinical practice for patients with OSA. The risks associated with this treatment are limited to the potential for slight discomfort associated with the use of a nasal/direct nasal mask during sleep. This has been mitigated with the pre-clinical testing, as described in the IB. Reporting of adverse events or adverse device effects will be included in the [redacted]

6. Justification for a Clinical Trial

6.1. Synopsis

This clinical investigation is designed to evaluate the performance (treatment efficacy and leak), comfort (subjective feedback), stability (subjective feedback, leak) as well as the participant's overall acceptance of the Nasal mask amongst OSA participants. An important factor in this investigation will be the testing of all four seal sizes (small, medium, large and wide) as well as other changes and improvements made to the design of the mask from the previous two clinical trials (Clinical trial 5 USA- CIA-195 & Clinical Trial 6 - NZ – CIA-205).

Up to 45 OSA participants who currently use a nasal or nasal pillows CPAP mask will be recruited by Clinical Trials of Florida from their database of patients. (Phone script for recruiting in Appendix A).

This study will involve a baseline visit (Visit 1) where the patient's prescribed PAP therapy treatment settings will be gathered. An F&P ICON+ device will be issued to the participant (if required) during this visit as well as gaining their informed consent for the F&P Nasal mask (CIA-211) and the Anthropometric 3D Scanning study (CIA-107). This will be followed by the participants being fitted with the F&P Nasal mask during visit 2 as well as being asked a few questions in the form of a structured questionnaire. Their initial impressions, comments and photographs will be captured via recorded audio and video (with their consent). Visit 2 will take place 7 ± 5 days after Visit 1. The [redacted]

patients will come in for a final visit to return the trial mask and documentation and provide their feedback in the form of verbal comments and a structured questionnaire. Photographs will be captured as well as audio and video recorded during this visit. Visit 3 will take place 14 ± 5 days after Visit 2.

The mask and CPAP (if from the research pool) will be returned to the Institution at the conclusion of the trial and the participant will return to their previous mask and mode of device treatment. The Institution will recruit all patients within two weeks of the beginning of the study.

[figure not shown]
[figure not shown]
This study will be conducted in accordance with ICH/GCP Guidelines. No deviation from the protocol will be implemented without the prior review and approval of the sponsor except where it may be necessary to eliminate an immediate hazard to a research participant. In such case, the deviation will be reported to the sponsor as soon as possible.

6.2. Literature Review

Obstructive Sleep Apnea (OSA) is a common sleep breathing disorder affecting up to 9% of the adult population¹ and is characterized by periodic collapse of the upper airway during sleep. The standard treatment for obstructive sleep apnea is PAP, which consists of pressurized air applied to the nose via an interface. PAP includes continuous positive airway pressure (CPAP), automatic positive airway pressure (APAP) and Bilevel positive airway pressure (Bilevel PAP). Despite the effectiveness of PAP in abolishing upper airway obstruction, acceptance of and adherence with therapy has been sub-optimal^{2,3}. Reasons for the low compliance include nocturnal awakenings, incorrect therapeutic pressure and primarily discomfort due to poor mask fit. Poor mask fit can result in facial abrasion, leak causing fluctuations in therapeutic pressure and irritation of the eyes^{4,5}.

6.3. Preclinical Testing

6.4. Previous Clinical Experience

6.5. Justification for Administration

Participants will remain on their prescribed PAP pressure during the duration of the trial. Baseline PAP data on the participant's usual mask will be collected for up to 2 weeks in order to evaluate leak measurements and efficacy of treatment compared to the investigational mask. Participants will not be randomised to use the F&P Nasal in-home for 14 ± 4 days.

7. Objectives of the Clinical Investigation

7.1. Hypothesis

7.2. Objectives

Primary Objective:

- To evaluate the performance, comfort and ease of use of the F&P Nasal mask in a home environment in regards to the participants' view on overall comfort, overall experience and satisfaction.
- To gain usability insights into mask fitting and removal from all participants enrolled in this mask study.

7.3. Population

Up to 15 participants will be recruited for the trial from Fisher & Paykel Healthcare, Auckland. These include current nasal mask users.

7.4.

7.5. Essential Requirements of the Relevant Directive

Essential requirements are not applicable since this study is being conducted in the USA only.

8. Clinical Investigation Design

8.1. Type of Investigation

This is an open-label (investigators and participants are un-blinded and informed of intended treatment device) single arm study. The intended treatment F&P Nasal mask will not be randomized – as the intention is not to compare between therapies.

8.2. Controls

The PAP device data gathered from the participants using their usual mask at baseline will act as the control for each participant, and it will be compared to the data gathered from the F&P Nasal mask.

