8.11. Withdrawal Criteria

Participants will be informed that they have the right to withdraw from the study at any time, without prejudice to their medical care, and are not obliged to state their reasons. The participants are informed that they can revert back to their usual therapy during the clinical investigation if they have reason to do so. Additionally the investigator may withdraw a patient at any time for the following reasons:

- Protocol Violation
- Safety concerns
- Serious illness
- Adverse event

The reason for participant discontinuation in the study is to be recorded in the CRF and source document.

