9.5. Description of the Statistical Design

Since the trial is regarding the performance and acceptability of the trial device in order to inform product development, no statistical design is required.

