9.9. Statistical Procedure Deviations

Statistical procedure deviations will be reported to the principal investigator and the sponsor. Deviations from the original statistical plan will be explained in the final study report.

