9.10. Selection Criteria

All participants who consent, and are fitted with a mask that they attempt to sleep on will be included in the analysis. Please see section 8.10 for information on participant flow throughout the trial.

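### Does the promised comparison with the usual mask need a stated method and a rule for which nights count?

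*Combined protocol and SAP*

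**What the plan says.** Section 8.2 says: "The PAP device data gathered from the participants using their usual mask at baseline will act as the control for each participant". It adds of those data that "it will be compared to the data gathered from the F&P Nasal mask". Section 6.5 explains that baseline data are collected "in order to evaluate leak measurements and efficacy of treatment compared to the investigational mask". Section 8.4.1 lists the PAP download, with questionnaires and the logbook or sleep diary, as a source for the primary-outcome bullet on ease of use, acceptance and adequate treatment.

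Section 8.1 explains the absence of randomisation "as the intention is not to compare between therapies". Section 9.5 says "no statistical design is required", because the study informs product development. Section 9.9 nevertheless says: "Deviations from the original statistical plan will be explained in the final study report".

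On who and what is analysed, Section 8.11 tells participants that "they can revert back to their usual therapy during the clinical investigation if they have reason to do so". Section 9.10 says that consenting participants who are "fitted with a mask that they attempt to sleep on will be included in the analysis". The Section 8.10 schedule issues the sleep diary at Visit 2 and, at Visit 3, collects it and downloads the PAP data. Visit 3 falls 14 ± 5 days after Visit 2 in Section 6.1, while Section 6.5 gives in-home use as 14 ± 4 days.

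**The concern.** Read together, these sections seem to promise a within-person comparison and then decline to say how it is made. No summary measure, paired method or interval is visible. Section 9.9 points to a statistical plan whose existence Section 9.5 appears to deny, and Section 8.1 can be read as disowning any comparison.

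The second worry is about nights. Participants may revert to their usual mask, one attempted night is enough for inclusion, and there is a single download after the in-home period. If that download were averaged whole, usual-mask nights would sit on the trial-mask side and pull the paired difference toward zero, whichever mask is better. Section 11 allows the results to be used in regulatory documents on clinical efficacy, so a diluted or loosely defined comparison could matter outside the sponsor's own development work.

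**Working it through.** **1. Is there a rule that mixes nights?** Section 8.2 restricts the trial side to data gathered from the F&P Nasal mask, so counting usual-mask nights there would contradict it. Section 9.10 selects people and says nothing about pooling nights. The reversion sentence in Section 8.11 sits under withdrawal, and may describe leaving the trial mask rather than alternating masks. The diary covers the same period as the download, and Section 8.4.1 names both for the same outcome. Mixing is a possibility; no visible passage calls for it.

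**2. Does Section 8.1 contradict Section 8.2?** In a single-arm study, the natural reading of Section 8.1 is that no between-arm comparison is intended. A descriptive comparison with each person's own baseline is compatible with that.

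**3. How large would dilution be if the nights were pooled?** The plan states no figure for this comparison, so there is none to reproduce. Let B be the baseline mean, T the true trial-mask mean, and f the share of a participant's in-home nights on the usual mask, assumed to resemble baseline:

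(1 − f)T + fB − B = (1 − f)(T − B)

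The share kept is 1 − f. With 14 nights (Sections 6.1 and 6.5), per person:

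- 1 usual-mask night: 1 − 1/14 = 0.929
- 4 nights: 1 − 4/14 = 0.714
- 7 nights: 1 − 7/14 = 0.500
- 13 nights, the extreme that Section 9.10 allows: 1 − 13/14 = 0.071

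For the group, assume 30 analysed (the target in Section 9.6), equal true differences, and m people reverting. The share kept is 1 − (m/30)f:

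| Usual-mask nights of 14 | m = 1 | m = 3 | m = 6 |
|---|---|---|---|
| 4 | 0.990 | 0.971 | 0.943 |
| 7 | 0.983 | 0.950 | 0.900 |
| 13 | 0.969 | 0.907 | 0.814 |

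For scale, the 95% confidence half-width for a paired mean with n = 30 is t/√n = 0.37 SD of the within-person differences. Take a true difference of 0.53 SD, which 30 pairs detect with 80% power at an assumed two-sided 5% level. The loss at m = 6 and 4 nights is (1 − 0.943) × 0.53 = 0.03 SD. In the most extreme cell it is (1 − 0.814) × 0.53 = 0.10 SD. Both are well inside the random error.

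**4. Would a rule keeping only diary-confirmed nights be cleaner?** It carries a bias of its own. Suppose the 4 dropped nights are those that would have had the highest trial-mask leak. With independent normal nights, the mean of the remaining nights is too low by 0.65 night SD if the period is 9 nights, 0.45 if 14, and 0.35 if 19. These lengths span the Section 6.1 window (14 − 5 = 9, 14 + 5 = 19). With 6 of 30 people affected, the group shift is 6/30 × 0.65 = 0.13 night SD at 9 nights and 6/30 × 0.45 = 0.09 at 14. These are illustrations, not upper bounds: skewed leak values would give more.

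**5. The windows.** 14 ± 5 is 9 to 19 days and 14 ± 4 is 10 to 18 days. A Visit 3 on day 9 or day 19 meets Section 6.1 but not the period in Section 6.5. Neither figure enters a stated analysis.

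**The case for a change.** The strongest case for a change is that a descriptive comparison also needs a defined measure and a defined set of nights. Without them the choice is made after the data are seen, and the usual-mask comparison is the study's only controlled, device-recorded evidence. Naming a paired difference and confirming one diary field would cost little.

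Part of this stands. No summary measure is visible, and Sections 9.5 and 9.9 sit awkwardly together. It does not carry the conclusion, for three reasons. The night set is not left open in principle, because Section 8.2 fixes it, and a diary is already issued with which to apply it. The diary form, the detailed visit descriptions, Sections 7.1, 8.6 and 9.7, and the plan mentioned in Section 9.9 cannot be seen, so a rule or method absent from the visible text cannot be taken as absent from the plan. Finally, the comparison is secondary in weight: Section 7.2 frames the objective around participants' views and usability, Section 9.6 sizes the study for finding usability problems, and the download is one of three sources for one of three primary-outcome bullets. A prescribed interval or named efficacy index would be a reviewer's preference here.

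**Conclusion.** No change to the plan follows. Applied as written, Sections 8.2 and 6.5 give a sound descriptive within-person comparison. The unnamed summary measure and the unstated night rule are details that analysts would fill sensibly. Section 8.1 is at most loosely worded.

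The possible harm depends wholly on assumed reversion and on nights being pooled against Section 8.2. On those assumptions, with 30 analysed and equal true differences, 94% to 99% of the group difference survives when 1 to 6 people each spend 4 of 14 nights on the usual mask, and 81% survives in the most extreme case considered. With no reversion, nothing is lost. A single participant's difference could shrink much more, but the plan rests no decision on an individual's PAP difference in the text that can be seen.

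The in-home windows in Sections 6.1 and 6.5 do disagree and must be reconciled. That is a clerical correction with no effect on a stated analysis or conclusion.

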8.3. Bias

The F&P Nasal mask is non-blinded and distinguishable. Since the trial mask is the same for the entire population, this study is not blinded.

8.4. End Points

8.4.1. Primary Outcomes

Primary Outcome:

- The F&P Nasal mask is comfortable to use for the participant as measured by the custom questionnaires and recorded during the interviews.
- The mask is easy to use, accepted by the participant and provides adequate treatment for OSA during in-home use measured via custom questionnaires, logbook/sleep diary and PAP data download.
- The acceptability of the F&P Nasal through custom questionnaires

8.4.2. Secondary Outcomes

- Seal size determination using the sizing tool
- To obtain 3D face scanning and head measurements to assist with future product development (CIA-107)

8.5. Variables

Variable	Justification
Ease of use/Acceptability	To assess the ease of using the mask in the home and overall mask acceptability
Mask Comfort	To assess the comfort (or lack of) of the mask as experienced by the participant while using it in-home.
Usability of the mask	To evaluate the usability of the Nasal mask through a custom designed ease of use usability script
General Demographics	To gather participants general demographics

Preference	To assess which mask the participants prefers to use going forward.	
Mask performance	To assess the mask's performance in relation to leak	
Seal selection size	To assess a way to determine best size of seal for participants	
Anthropometric	To assist with future product development	

8.6. Measurements

[figure not shown]

Figure 2. Back strap landing length measurement

8.7. Equipment

Participants will be issued a F&P ICON+ Premo/Auto machine (if required) for baseline data. This device is a market-released device which is supplied with a released user manual. The participants will only be issued an ICON+ device if their current device cannot record efficacy data, leak data or have removable storage (SD card or USB stick).

8.8. Inclusion / Exclusion criteria

Inclusion Criteria

- AHI ≥ 5 from the diagnostic night
- ≥ 18 years of age
- Either prescribed APAP, CPAP or Bi-level PAP for OSA
- Existing nasal or nasal pillows mask users (ideally a 70%:30% split)
- Fluent in spoken and written English

Exclusion Criteria

- Inability to give informed consent
- Patient intolerant to PAP
- Anatomical or physiological conditions making PAP therapy inappropriate
- Current diagnosis of respiratory disease or CO₂ retention
- Pregnant or think they may be pregnant

8.9. Point of Enrolment

[figure not shown]
Participants will be recruited from patients who are prescribed either APAP, CPAP or Bi-level PAP for OSA at Clinical Trials of Florida. The principal investigator (or those identified in delegation log) will ask the subjects whether they're interested to take part in the trial. The patients who provide informed consent and meet the inclusion/exclusion criteria will then be enrolled into the trial.

8.10. Patient Procedure

The study coordinator will ask the subjects whether they're interested to take part in the trial. Only eligible participants, that provide written informed consent, will be enrolled into the investigation.

[figure not shown]
[figure not shown]
EVENTS	Visit One	Visit Two	Phone Call	Visit Three
Informed consent	X			
ICON+ Premo/Auto given and instructions for use (if applicable)	X			
Commence baseline data gathering	X			

Participant Questionnaire (see Appendix)		X		
Mask fitting with F&P Nasal mask		X		
Head Measurements		X		
Static Leak Measurement		X		
Issue Sleep Diary (Appendix F)		X		
Issue complete Nasal mask with UI		X		
Researcher Questionnaire (see Appendix B)		X		
Baseline PAP device data downloaded		X		
Commence in-home trial of the F&P Nasal mask		X		
Phone call				X
Return the F&P Nasal mask				X
Returned loaned ICON+ Premo/Auto given and instructions for use (if applicable)				X
Return Sleep Diary				X
Participant Questionnaire (see Appendix)				X
Researcher Questionnaire (see Appendix B)				X
PAP device data downloaded				X

With the following section, the days ($\pm N$) reflects: the date that will begin for that section (\pm the range within which the visit is acceptable).

Clinical Trials of Florida will be providing compensation to the participant of \$40.00USD for each completed visit (a total of \$120USD for 3 visits). This will be paid after the conclusion of each visit or the withdrawal of the participant from the trial during any of the visits.

8.11. Withdrawal Criteria

Participants will be informed that they have the right to withdraw from the study at any time, without prejudice to their medical care, and are not obliged to state their reasons. The participants are informed that they can revert back to their usual therapy during the clinical investigation if they have reason to do so. Additionally the investigator may withdraw a patient at any time for the following reasons:

- Protocol Violation
- Safety concerns
- Serious illness
- Adverse event

The reason for participant discontinuation in the study is to be recorded in the CRF and source document.

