9.6. Sample Size

From the 'Guidance for Industry and Food and Drug Administration Staff – Applying Human Factors and Usability Engineering to Optimize Medical Device Design' document issued on 3 February 2016, a number of 30 users will be sufficient to find a minimum of 97% of problems and on average can find 99% of all problems¹³. Additionally from previous experiences, a number of 30 users was not quite achieved when taking into account drop outs and no shows hence the recruitment drive for up to 45 participants has been set. .

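### Post-use outcomes are scheduled only at Visit 3 and no early-exit assessment is specified, so the primary results may in effect rest on Visit 3 attenders

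*Combined protocol and SAP*

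**What the plan says.** - **Analysis set (9.10).** "All participants who consent, and are fitted with a mask that they attempt to sleep on will be included in the analysis". Attendance at Visit 3 is not a condition.
- **Primary outcomes (8.4.1).** The comfort outcome reads "The F&P Nasal mask is comfortable to use for the participant as measured by the custom questionnaires and recorded during the interviews", with no time point. The second outcome asks that the mask is easy to use, is accepted and "provides adequate treatment for OSA during in-home use measured via custom questionnaires, logbook/sleep diary and PAP data download".
- **Schedule (8.10).** The row "Commence in-home trial of the F&P Nasal mask" is marked at Visit 2. After that, the second participant and researcher questionnaires, the diary return and the second PAP download are marked only under Visit Three. The PAP download at Visit 2 is baseline data on the usual mask. There is a Phone Call column, but in the text as supplied the call itself is marked under Visit Three and its content is not described.
- **Final feedback (6.1).** At the end of the home period, "patients will come in for a final visit to return the trial mask and documentation and provide their feedback". Visit 3 falls 14 ± 5 days after Visit 2.
- **Withdrawal (8.11).** "The reason for participant discontinuation in the study is to be recorded in the CRF and source document", but participants "are not obliged to state their reasons". The same section lets participants return to their usual therapy during the study and does not call this withdrawal.
- **Expected losses (9.6).** In earlier work, "a number of 30 users was not quite achieved when taking into account drop outs and no shows", so up to 45 are to be recruited. No loss rate is given.
- **Missing data.** The readable text has no rule for missing outcomes. Section 9.5 states that a statistical design is not needed.

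**The concern.** Sections 8.10, 8.11 and 9.10 do not fit together. Suppose a participant sleeps in the mask for two nights, finds it uncomfortable, withdraws and does not come back. Section 9.10 counts that person in the analysis, but no scheduled assessment supplies a post-use value.

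This matters because leaving is unlikely to be unrelated to the outcome. Discomfort and leak are plausible reasons both for stopping and for a poor rating. If the post-use summaries use whoever has data, they will probably look better than the experience of everyone who tried the mask. Recruiting up to 45 protects the count of 30 but does not remove this selection, because people who left over the mask are replaced by people who tolerate it. That also weakens the problem-finding purpose for which 30 users was chosen. Section 11 leaves open the use of the results in marketing and regulatory documents, so a favourable tilt could travel beyond product development.

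**Working it through.** **1. The plan's own figures.** Section 9.6 says 30 users find at least 97% and on average 99% of problems. It gives no detection probability per user, so these figures cannot be reproduced. Under 1 − (1 − p)^30, 97% corresponds to p = 0.110 and 99% to p = 0.142. The step from 30 to 45 has no stated loss rate. It corresponds to 1 − 30/45 = 33.3%, since 30/(1 − 1/3) = 45. That rate is back-calculated, so it does not check the figure. The point here disputes neither number.

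**2. What a participant has after leaving between Visits 2 and 3.**

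| Item | Available under the readable text? |
|---|---|
| Visit 2 questionnaire and first impressions | Yes, but collected before any home use |
| Reason for leaving | To be recorded; may be withheld |
| Clinically significant adverse events | Yes (section 10) |
| Post-use questionnaires | Scheduled at Visit 3 only |
| Diary | Returned at Visit 3 only |
| Trial-mask PAP data | Downloaded at Visit 3 only |

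**3. How many could be affected.** Take 45 recruits (6.1, 8.12 and 9.6; section 7.3 gives a different number) and assume the target of 30 attend Visit 3. Then 45 − 30 = 15 is the ceiling. It is an upper bound because section 9.6 counts no-shows as well as drop-outs, and anyone lost before fitting never enters the 9.10 set.

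**4. Effect on an acceptability proportion.** With 30 attenders, s of them favourable, and m early leavers without data:

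- lowest full-set value = s/(30 + m), if every leaver is unfavourable;
- highest full-set value = (s + m)/(30 + m), if every leaver is favourable.

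Assume s = 24, so the attender figure is 24/30 = 80%. The 24 is an assumption; the plan gives no expected rate.

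| m | Lowest | Highest |
|---|---|---|
| 3 | 24/33 = 72.7% | 27/33 = 81.8% |
| 6 | 24/36 = 66.7% | 30/36 = 83.3% |
| 10 | 24/40 = 60.0% | 34/40 = 85.0% |
| 15 | 24/45 = 53.3% | 39/45 = 86.7% |

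The width is m/(30 + m) whatever s is: 9.1 points at m = 3 and 33.3 points at m = 15. Varying s moves the range. At m = 15, an attender figure of 70% (s = 21) gives 46.7% to 80.0%, and 90% (s = 27) gives 60.0% to 93.3%.

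**The case against.** The strongest reply is that stopping the mask is not the same as leaving the study. Section 8.11 allows a return to usual therapy, and someone who does that can still attend Visit 3, fill in the questionnaire and hand over the diary and device data. Section 8.10 also foresees withdrawal at a visit, since it provides for payment in that case. This stands, and it narrows the gap to participants who withdraw and do not return. For them, diary entries or stored device data might be recoverable, but nothing readable requires anyone to retrieve them.

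Some relevant text is also not available: the visit-by-visit details announced after the 8.10 table, two figures there, and the appendices, including an exit interview questionnaire listed in the contents. An early-exit step could sit in any of these. That limits confidence but leaves the silence in 8.11 as it is.

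Three stronger readings are tempting and should be resisted:

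- A reader might infer that the plan restricts the primary result to completers. No section says so, and 9.10 says otherwise. The restriction would arise in practice, through missing data.
- A reader might infer that early leavers have no outcome data at all. Everyone fitted has Visit 2 impressions, and the comfort outcome includes interviews without a stated time point. Those impressions precede home use, however, so they cannot stand in for in-home comfort or treatment.
- A reader might infer that problems serious enough to cause withdrawal go unrecorded. Reasons and clinically significant adverse events are to be recorded; a reason may be absent, but it is not absent by design.

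Finally, this is a product-development study without a formal statistical design. That argues against elaborate missing-data methods. It does not argue against asking people why and how the mask failed them.

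**Conclusion.** The concern holds in a limited form. On the readable text, participants who withdraw between Visits 2 and 3 remain in the analysis set and may lack every post-use primary measure. The post-use results may then in effect describe Visit 3 attenders. The likely direction favours the mask; that is a judgement about why people stop, which the documents do not establish.

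The size is uncertain, and the bounds run both ways. A reader might treat all 15 possible losses as fitted participants who left because of discomfort and quote a single large overstatement. The documents do not support that: no-shows are among the 15, and neither the reasons for leaving nor an expected acceptability rate is given. The bounds rest on three assumptions: 30 attenders, an illustrative 80% among them, and 3 to 15 early leavers without data. The problem should be corrected before the study starts. Confidence is moderate, because part of the visit-level text was not available.

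**What to change.** 1. **Collection.** In 8.11, and in a footnote to the 8.10 schedule, state that anyone who stops the trial mask or withdraws after Visit 2 is offered the existing Visit 3 assessments at that time, in person or by phone: exit questionnaire, diary return and PAP download. Taking part stays voluntary. If the visit details or appendices already provide this, a cross-reference in 8.11 is enough.
2. **Reporting.** Give the number with post-use data against the full 9.10 set. Report acceptability on that denominator, with mask-related stopping as its own outcome category. Counting those participants as not accepting the mask is an equally sound convention, provided the choice is stated in advance. Show the Visit 3 attender figure beside it, with best-case and worst-case bounds for anyone still missing.

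The cost is a sentence in 8.11, a schedule footnote and a short reporting rule, using forms that already exist. The downside is a few early exit calls or visits and possibly a less favourable figure.
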